## 3. OTHER EXPLORATORY OUTCOME VARIABLES MEASURED DURING THE FOLLOW-UP PERIOD (18-48 MONTHS):

- a. Time to 4th wheezing episode.
- b. Annualized number of days with wheezing.
- c. Annualized number of days with parental absence from work due to child's respiratory symptoms.
- d. Annualized number of days with child absence from day care.
- e. Annualized number of days with nights with awakening due to respiratory symptoms.
- f. Rates of ED and urgent care visits.
- g. Rates of hospitalizations for respiratory symptoms.
- h. Rates of upper respiratory infections.
- i. Proportion of children prescribed asthma controllers medications (ICS, LTRA).
- j. Cumulative number of wheezing episodes.
- k. Proportion of children with at least one positive specific IgE (SIgE) to inhalant allergen at V3 and at the end of study visit (see Section O for details on the specifics allergy testing).
- l. Total IgE level and eosinophil count measured at the last study visit.
- m. Determine if demographic (sex, age, race), baseline asthma/allergy phenotypic characteristics (Personal/family atopic history, second hand smoking, pet exposure), RSV serotype (A vs. B), peripheral eosinophil count, and the presence of co-infection with other respiratory viruses during the RSV bronchiolitis (e.g. rhinovirus) and/or bacteria are predictors of response to azithromycin therapy.
- n. Changes in upper airway microbiome community structure following study treatments.
- o. Upper airway microbiome community structure measured 6 months following randomization.
- p. Based on our preliminary data we will specifically evaluate if azithromycin therapy results in reduction of *Moraxella* abundance and whether lower *Moraxella* abundance is associated with reduced odds to develop RW.
- q. Compositions of the viral and/or the fungal components of the upper airway microbiome, and the composition of the stool microbiome (these will be explored based on availability of additional funding).

Secondary clinical outcomes will be assessed by clinic visits and phone call interviews as described for the primary outcome. These will be measured as we previously described.

#### **4. LABORATORY OUTCOMES MEASURED AT ENROLLMENT AND AT THE END OF THE 2-WEEK STUDY TREATMENT PERIOD:**

- a. Nasal lavage levels of IL-8.
- b. Nasal lavage levels of neutrophil elastase.
- c. Nasal lavage levels of matrix metalloproteinase 9 (MMP-9).
- d. Rates of upper airway colonization with macrolide-resistant bacteria (additional sampling at the 6 month clinic visit). See Section O for the specifics of macrolide-resistance studies.

## G. RANDOMIZATION

Patients who satisfy all the eligibility criteria at RZ encounter will be randomized to azithromycin or placebo groups based on a blocked randomization allocation sequence. Randomization list will be supplied to the investigational pharmacy at SLCH by the study statistician. Randomization will be stratified by prior use of open-label non-macrolide antibiotic over the past 2 weeks prior to randomization. The investigators will be blinded to treatment assignment and to the size of randomization blocks. Hence, size of randomization blocks will be randomly selected by the randomization software. Once all data collection has been completed study medications will be dispensed.

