### C. EXCLUSION CRITERIA

1. Prematurity (gestational age < 36 weeks).
2. Presence or history of other significant disease (CNS, lung, cardiac, renal, GI, hepatic disease, hematologic, endocrine or immune disease). Children with atopic dermatitis and/or food allergy will not be excluded from the study.
3. Clinically significant gastroesophageal reflux currently treated with a daily anti-reflux medication (anti- H2 or PPI).
4. The child has significant developmental delay/failure to thrive, defined as weight < 3% for age and gender.
5. History of previous (before the current episode) wheeze or previous (before the current episode) treatment with albuterol.
6. History of previous treatment with corticosteroid (systemic or inhaled) for respiratory issues. This criterion was included to identify children who may wheezed in the past.
  - a. Prior treatment with systemic corticosteroids for non-respiratory issues (e.g., eczema, food allergy) will not exclude the child from participation in this study.
  - b. Although corticosteroids are not recommended by the American Academy of Pediatrics as a therapy for RSV bronchiolitis, it might be that some RSV patients will be treated with corticosteroids. Such a therapy during the current acute RSV bronchiolitis (but not before this illness) will not exclude the child from participation in this study.
7. Treatment (past of present) with montelukast.
8. Treatment with any macrolide antibiotic (azithromycin, clarithromycin or erythromycin) over the past 4 weeks or current treatment with any macrolide antibiotic. Current or prior treatment with

non-macrolide antibiotic is not an exclusion criterion (unless this antibiotic is included in the list of medications that may cause QT interval prolongation- see #16 below). The use of topical antibiotics, including topical macrolides (e.g., ear/eye drops and eye ointments) is NOT an exclusion criteria.

9. Chronic treatment with any daily medication other than vitamins or nutritional supplements. Although routine vitamin D supplement (400 IU per day) is not an exclusion criterion, high dose vitamin D supplements are not allowed. Other allowed medications include: topical medications (e.g., topical corticosteroids), allergy (anti-h1) medications, ear/eye drops.
10. Participation in another clinical trial.

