### 1. Enrollment and Randomization visit (RZ) during the acute hospitalization:

- a. Eligibility determined based upon inclusion and exclusion criteria.
- b. Informed consent obtained.
- c. Release of medical data obtained.
- d. Provide an information brochure about the study (will include study ID, contact phone number of the investigators, instruction to avoid any macrolide antibiotic during the 2 weeks of study therapies). A copy of this brochure will be send to the primary care physician.
- e. Detailed family history and environmental allergy questionnaires obtained.
- f. Medical history obtained.
- g. Study physical examination including height and weight performed. This physical exam is performed to assure the child can participate in the study. **This exam has different goals than the physical exam performed by the child's attending physician as a standard of care, and cannot replace the attending's exam.**
- h. Document the administration over the past 24 hrs of: supplemental oxygen, IV fluids, albuterol or other bronchodilators, antibiotics.
- i. Calculate bronchiolitis severity score.
- j. Provide education about study medications, and discuss the need to avoid any macrolide antibiotic during the active phase of the study.
- k. Provide and teach Study Medication Diary (This paper diary monitor for study medications adherence and potential side effects) completion.
- l. Obtain baseline blood, stool, nasal wash and nasal brush samples, and urine (if able to obtain while child is hospitalized).
- m. Dispense first batch of study medications and dosing syringes. Teach study medication administration.
- n. Coordinate study medication delivery with the nursing staff of the inpatient unit.
- o. Schedule the clinic follow up visit (V1).
- p. Obtain contact information (including e-mail if available) and preferred time for follow up telephone calls (PCs).
- q. Provide/arrange for parent's compensation.
- r. If a Respiratory Pathogen Multiplex PCR testing has been performed in SLCH, document the presence of other respiratory viruses (if not done, this will be performed at the end of the RSV season on a nasal wash sample).

### 2. Daily follow up during the acute hospitalization (HSP1, HSP2 etc...):

- a. Review Study Medication Diary card.
- b. Review study medication treatment and adherence.

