- c. Remind date of clinic follow up visit (V1) and the need to bring study medication bottle to the visit. Dispense materials for collection of stool sample before the V1 visit.
- d. At the end of hospitalization document the following: supplemental oxygen (days), IV fluids (days), albuterol or other bronchodilators, hypertonic saline inhalations, antibiotics, oral steroids, inhaled steroids, montelukast, length of hospitalization (days).
- e. Schedule the date for the MED1 phone call and the date/time for the delivery of the second bottle of study medications (for the 2nd week 2 of the study treatment).

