### Primary outcome analysis:

The initial analytic strategy will be a log-rank test, which compares the Kaplan Meier survival curves describing the time to the third episode of wheezing.

Then, the primary analysis of the primary endpoint will be conducted using a stepwise Cox regression model that would include 2 covariates: race and parental history of asthma. These 2 covariates were significant predictors of childhood asthma development following severe RSV bronchiolitis in our RBEL cohort. If the proportional hazards assumption is violated, we will follow the recommendations of Allison and will address the problem by including in the model an interaction term between time and the variable that violates the proportional hazards assumption.

At the next step, we will conduct multivariate analysis that will include other covariates that may be associated with the primary outcome. Chi square tests, t-tests, and potentially Wilcoxon's test will be used to compare all non-time dependent covariates listed below\* across groups in order to identify variables that should be included in subsequent multivariate models. Those fixed-time covariates that yield at least some suggestion of a between-group difference ( $p < 0.1$ ) will then be included in a stepwise Cox regression analysis along with all of the time dependent covariates (e.g., pet exposure). Additional analyses will include the use of an Anderson-Gill model in which wheezing episodes are treated as recurrent events when compared between groups. In Cox models that do not contain time dependent covariates, we will evaluate the proportional hazards assumption by assessing the parallelism of the log-log plots and using martingale residuals and the method of Lin, and Ying. The Cox models which contain time-dependent covariates will be tested using Schoenfeld residuals.

The key statistic to be generated by the Cox regression analyses, for primary outcome reporting, will be covariate adjusted hazard rate ratios that compare the RW hazard rate in the azithromycin group with the corresponding hazard rate in the control group. Ninety-five percent confidence bounds will be generated for all calculated hazard rate ratios.

Finally, we will explore for potential interactions between study treatment assignment and pre-specified covariates to evaluate whether these covariates are predictors of response to azithromycin therapy:

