- a. Demographic: Sex, age, race.
- b. Baseline asthma/allergy phenotypic characteristics: Personal history of eczema, parental history of asthma, peripheral eosinophil count on enrolment.
- c. Environmental phenotypic characteristics: second hand smoking, pet exposure.
- d. Acute bronchiolitis characteristics: Duration of respiratory symptoms before enrolment, and the presence of co-infection with other respiratory viruses during the RSV bronchiolitis (e.g. rhinovirus).

\*The following covariates will be compared between the groups and would be considered to be included in the Cox models:

- a. Age at enrollment (months)
- b. Gender
- c. Race
- d. Birth weight
- e. Length of pregnancy (wks)
- f. Maternal smoking status during pregnancy
- g. Breast feeding status at the time of enrollment

- h. Tobacco smoke exposure (at the time of enrollment and during f/u visits)
- i. Pet exposure (at the time of enrollment and during f/u visits)
- j. History of eczema
- k. Parental history of asthma
- l. Duration of respiratory symptoms prior to randomization
- m. Duration of hospitalization (hours: measured from the time of the Emergency Room visit that triggered the admission and until time of discharge)
- n. Lowest O2 saturation recorded on room air
- o. Antibiotics use during the acute hospitalization. Antibiotic use during the follow up period will be measured as one of the secondary outcomes.
- p. Co-infection with other respiratory virus on enrollment (mainly Rhinovirus)
- q. Complete compliance with study medication (defined as >80% compliance)
- r. Antipyretic (acetaminophen and Ibuprofen) use during the initial RSV bronchiolitis
- s. Day care attendance
- t. Number of siblings in the house
- u. Eosinophil count at enrollment

**Censoring considerations:** All subjects will be censored at the time of the last contact with the subject confirms that they had not experienced the outcome measure. This applies whether the subject is a dropout or has remained on study until the end.

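### The one factor used to stratify randomization is left out of the primary log-rank test and Cox model, and the only antibiotic covariate on the candidate list partly postdates randomization

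*Combined protocol and SAP*

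**What the plan says.** **Randomization.** Section V.G states: "Randomization will be stratified by prior use of open-label non-macrolide antibiotic over the past 2 weeks prior to randomization". Section II.E.1 repeats this, and no other factor is named. The factor varies among enrolled children because exclusion criterion 8 in section V.C bars recent macrolides but admits children on non-macrolide antibiotics.

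**Primary analysis.** Section VII.A (Primary outcome analysis) begins with a log-rank test and mentions no strata. The primary Cox analysis is a "stepwise Cox regression model that would include 2 covariates: race and parental history of asthma".

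**Later models.** The 21-item candidate list (a to u) in the same section has one antibiotic entry, item o: "Antibiotics use during the acute hospitalization". Fixed covariates on the list that differ between arms at p<0.1 go into a further stepwise Cox model. The sensitivity analyses add a LASSO selection over fixed covariates.

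**Data collection.** At the RZ visit (section V.E), item h reads: "Document the administration over the past 24 hrs of: supplemental oxygen, IV fluids, albuterol or other bronchodilators, antibiotics". Item f reads: "Medical history obtained". In-hospital antibiotics are recorded again under the daily hospital follow-up, item d: "At the end of hospitalization document the following: supplemental oxygen (days), IV fluids (days), albuterol or other bronchodilators, hypertonic saline inhalations, antibiotics".

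**The concern.** An analysis normally respects the way treatment was allocated. Stratified blocks balance the arms on prior antibiotic use. If that factor predicts recurrent wheeze, an unstratified test uses a variance that is too large for the design: it rejects too rarely under the null and loses power under the alternative. The trial's own rationale makes a prognostic role plausible, because it proposes that airway bacteria influence recurrent wheeze. The documents do not show such a role for prior antibiotics.

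A second, smaller issue is item o. A covariate measured partly after randomization can be affected by treatment, and adjusting for such a variable can bias the hazard ratio. The screen adds to this, since it selects on a between-arm difference rather than on association with outcome.

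**Working it through.** **1. The antibiotic variables side by side**

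| Place | Window | Role |
|---|---|---|
| V.G, II.E.1 | 2 weeks before randomization, non-macrolide | Stratification factor |
| V.E, RZ item h | Past 24 hours | Record of current care |
| V.E, daily hospital follow-up, item d | Documented at end of stay | In-hospital treatment record |
| VII.A, item o | The acute hospitalization | Candidate covariate |

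Randomization takes place during the stay (inclusion criterion 4 and the RZ visit), and treating physicians may prescribe antibiotics (section V.D). Item o therefore covers time on both sides of randomization. A course finished before admission but within 2 weeks of randomization puts a child in the stratum but not in item o. An antibiotic first given after randomization does the reverse.

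**2. The plan's own design figures**

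Section VII.B.1 gives monthly placebo hazards: 2% for months 1 to 3, rising to 5% at month 12, falling to 3% at month 24, then 2% in year 3 and 1% in year 4. With linear interpolation, 1 − ∏(1 − h) over 48 months is 71.1%, against 71.6% stated. The azithromycin monthly hazards are not given.
- A hazard ratio of 0.5 to month 24 and 1 afterwards gives 54.9%, against 55.1% stated. Power at 94 per group is then 0.74 to 0.83, depending on how the 20% dropout is handled.
- A hazard ratio of 0.34 to 0.36 to month 18 and 1 afterwards gives 54.9% to 55.5%. Power is then 0.91 to 0.89 at 94 per group with dropout spread over 48 months.

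So the stated 0.9 is attainable but not uniquely reproducible. Nothing below depends on it.

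**3. Effect of ignoring the stratum**

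The simulation used 188 children, blocks of 4 within stratum, a two-sided 0.05 test, a treatment hazard ratio of 0.5 to month 24 and 1 afterwards, and 8,000 runs per cell. Both tests were applied to the same data. The prevalence of prior antibiotic use and its prognostic hazard ratio are assumptions.

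| Prevalence | Prognostic HR | Type I error, unstratified / stratified | Power, unstratified / stratified |
|---|---|---|---|
| 20% | 1 | 0.050 / 0.050 | 0.798 / 0.799 |
| 20% | 1.5 | 0.048 / 0.051 | 0.796 / 0.802 |
| 20% | 2 | 0.045 / 0.050 | 0.776 / 0.795 |
| 20% | 3 | 0.037 / 0.049 | 0.718 / 0.778 |
| 40% | 1 | 0.049 / 0.048 | 0.804 / 0.805 |
| 40% | 1.5 | 0.048 / 0.049 | 0.791 / 0.801 |
| 40% | 2 | 0.045 / 0.050 | 0.767 / 0.793 |
| 40% | 3 | 0.035 / 0.051 | 0.702 / 0.780 |

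The Monte Carlo standard error is √(0.8 × 0.2 / 8000) ≈ 0.0045 for power and √(0.05 × 0.95 / 8000) ≈ 0.0024 for type I error. Ignoring the stratum costs 0.6 to 1.0 points of power at a prognostic hazard ratio of 1.5, 1.9 to 2.6 points at 2, and 6.0 to 7.8 points at 3. At 1 there is no material difference.

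**4. When item o would pass the p<0.1 screen**

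- *No treatment effect on in-hospital antibiotics.* With stratum prevalence 20% to 40% and new use after randomization 0 to 20% (both assumed), item o passes in about 0 to 3% of simulated trials. This counts every child in the stratum as positive on item o. The less the two variables overlap, the closer the rate comes to the nominal 10%.
- *Treatment lowers use from 30% to 20% (assumed), 94 per group.* The pooled standard error is √(2 × 0.25 × 0.75 / 94) = 0.0632 and the unpooled one is √((0.21 + 0.16) / 94) = 0.0627. Power is Φ((0.10 − 1.645 × 0.0632) / 0.0627) ≈ 0.48.

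The screen is thus much more likely to admit item o when treatment has changed it. For the same reason, adding the stratum to the candidate list would not help: a factor balanced by design would rarely pass.

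**The case against.** The strongest reply is that randomization remains valid without a stratified analysis, that the error is in the conservative direction, and that the gain rests on unknown inputs. All of this stands. Section VII.A names race and parental asthma as the predictors found in the earlier cohort, and no passage links prior antibiotics to recurrent wheeze. The simulated power of about 0.80 is also not the plan's 0.9 design point, so the losses are illustrations.

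Three stronger readings are tempting and do not hold.
- **A reader might infer that item o replaces the stratum in the primary analysis.** It does not. The primary Cox model has two named covariates, and item o is only a candidate at a later step or in a sensitivity analysis. What remains is that section VII.A calls covariate-adjusted hazard ratios the key statistic for primary reporting without saying which model supplies them.
- **A reader might infer from RZ item h that the 2-week status was never collected.** Item h describes current care. The status had to be known in order to randomize, a medical history was taken, and criterion 8 required a check of "Treatment with any macrolide antibiotic (azithromycin, clarithromycin or erythromycin) over the past 4 weeks or current treatment with any macrolide antibiotic". A visit list is not a case report form.
- **A reader might infer that treatment does alter in-hospital antibiotic use.** Nothing in the documents says so. Treatment is blinded and the care pathway in section V.D discourages antibiotics. Bias from item o is conditional on such an effect.

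Other listed covariates, such as duration of hospitalization (item m) and compliance (item q), also extend past randomization. The general objection to that list is wider than this point.

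**Conclusion.** The omission is clear from the text: the sole stratification factor is in neither the log-rank test, nor the primary Cox model, nor the candidate list. The consequence is modest. There is no inflation of type I error: the simulated unstratified error runs from 0.050 down to 0.035, while the stratified test stays at 0.048 to 0.051. The power cost is nil if the factor is not prognostic, about 1 point at a hazard ratio of 1.5, and 2 to 3 points at 2. It reaches 6 to 8 points only at an assumed hazard ratio of 3. These figures assume a prevalence of 20% to 40%. No sample size in the plan changes.

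Item o is a poor adjustment variable because its window spans randomization, but any harm is confined to later adjusted models and depends on treatment affecting antibiotic prescribing. The point is best classed as a free improvement. It is not a threat to the trial's validity.

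**What to change.** Before unblinding:
1. In section VII.A (Primary outcome analysis), stratify the log-rank test and the primary Cox model by the randomization stratum. State that the stratum comes from the randomization records and is exempt from stepwise, p<0.1 and LASSO selection.
2. In the candidate list, remove item o or limit it to use before randomization. Removal is simpler, since prior use would add little once the model is stratified. Report in-hospital antibiotic use after randomization descriptively by arm.

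No change to the RZ form is needed: Appendix 2 reports that 200 participants had already been recruited. The cost is a few lines of SAP wording and one extra two-level stratum, which is negligible at about 200 children. In the simulation, stratifying cost no material power when the factor had no prognostic effect.

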## H. NON STUDY DRUGS

Chronic daily treatment with any medication other than routine vitamins or nutritional supplements, and other than current treatments for the acute RSV bronchiolitis will exclude the child from participation in the study.

Treatment with macrolide antibiotic (erythromycin, clarithromycin or azithromycin) will not be allowed during the active treatment phase of the study due to safety concerns of potential overdosing with macrolides; if this treatment will become mandatory, participation in the study will be terminated.

Other treatments (including antibiotics, inhaled corticosteroids, systemic corticosteroids, montelukast and albuterol) may be prescribed by the SLCH physician and/or the child's primary care physician by their clinical judgment, and will be recorded in the child's research file.

## I. RECRUITMENT

We will recruit up to 200 children over 3 consecutive RSV seasons. We have a sufficient pool of hospitalized RSV patients available for this study as approximately 400+ children, aged 1 month (30 days) -18 months, are admitted to SLCH each RSV season. Moreover, over 7 RSV seasons our group has recruited similar number of patients (~ 65 patient/season) in our institution for 2 observational RSV cohorts (RBEL I, II). The SLCH census list will be reviewed twice daily during the RSV season for all potential admissions with RSV bronchiolitis. Furthermore, all children with positive RSV results from the virology lab at SLCH will be identified twice daily to assess for potential eligibility. Based upon these initial screens, all hospitalized 1 month (30 days) -18 month old infants will be further screened by a study coordinator to determine eligibility. Recruitment and retention will be monitored yearly at the end of each RSV season to assure adherence to the accrual milestone as listed below.

	M1 May 1, 2017	M2 May 1, 2018	M3 May 1, 2019
Expected enrollment (for season)	57	66	65
Cumulative enrollment expected	57	123	200
Minimum enrollment	47 	118 	NA
Minimum retention of subjects enrolled in prior seasons	NA	80% 	80% 

